### **Inclusion Criteria**

- 40 years of age or older; and
- Able to read and write English; and
- Diagnosed with COPD (PFT values: FEV1/FVC <0.7 and FEV1% predicted < 80% - within the past 6 months); or Dyspnea score of greater than "2" on the Modified Medical Research Council (MMRC) questionnaire.

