### **Exclusion Criteria**

- Pregnant female or less than 1 year post-partum; or
- Diagnosed cognitive deficit or observed lack of understanding during the informed consent process; or
- Mobility impairment; or
- Lack of 3g WiFi access in place of residence; or
- Unwillingness to wear physical activity tracker daily, follow protocol, and/ or attend study visits.

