## 8.0 Recruitment Methods

Study recruitment flyers advertising the study will be posted within MUSC among general population patient clinic waiting room and elevator areas. Study recruitment will also take place in the clinics of MUSC and via referral during an admission for COPD exacerbation, or within the first 2 weeks after discharge. Any MUSC clinician who provide care to the target population can initially approach potentially eligible patients about the study, and if interested provide them with the contact details for the Study Team. With the patient's verbal permission, the provider may also provide the patient's contact information to the Study Team. Upon initial contact with the patient, patients will be verbally prescreened per the inclusion/exclusion criteria by our study team and given more information about the study. For those prescreened eligible and interested patients, and an informed consent meeting will be set-up at MUSC Nexus Research Center at the patient's convenience.

Additionally, for the purposes of this study and in direct alignment with the mission of the CON P20 Symptom Self-Management Center, we will employ the use of MUSC Bioinformatics Center (BMIC) core services to identify and recruit patients across the MUSC Enterprise that meet the study inclusion/exclusion criteria and that have granted authorized research contact permission in MyChart through the electronic 'opt in' EPIC designation. Once these potentially eligible patients are identified, we will then contact them by telephone using a script to determine if they are interested in study participation.

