## 10.0 Study Design / Methods

This is a randomized longitudinal controlled observational study using a mixture of qualitative and quantitative methods. The study will recruit 30 participants and utilize a control group experimental design with dependent pretest and posttest to derive data regarding (1) feasibility and (2) within-participant effect size of the RESP-FIT intervention in terms of satisfaction, use and adherence, technical issues and acceptability, and self-reported symptom severity (dyspnea and fatigue). In addition, information satisfying Exploratory Aim 4 (frequency of physical activity) will be obtained. Patient data (Table 1 below) will be collected at baseline, 6 weeks (post-treatment) and 14 weeks (2 month follow up). This study will enable further development of SAMS using our patient centered iterative design guided by feedback from a convenience sample. When completed, 30 adults (15 in each group) will have used SAMS for 6 weeks. (see Fig. 2 Study Design).

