**Figure 2: Feasibility Study of RESP-FIT with SAMS Report: Pilot Intervention with Quantitative/Qualitative Assessment**

**Participants:** Subjects will be 30 adults, aged 40 and older, with mild to moderate COPD, defined as a spirometric diagnosis of (FEV1/FVC <0.7 and FEV1 % predicted < 50%), with the ability to understand written and spoken English, and who report dyspnea greater than “2” on the Modified Medical Research Council (MMRC). Participants must be willing to continually wear a FitBit activity monitor, and have access to a smartphone or Wi-Fi/Data-enabled iPad and with willingness to download the FitBit and

SAMS apps. Participants without access to a smartphone or Wi-Fi/Data-enabled iPad may be loaned an iPad for the duration of their training and given comprehensive training on the use of the device. Pregnant females and females less than 1 year post-partum (via self-report) will be excluded, as pregnancy affects fatigue and the perception of dyspnea due to increased abdominal pressure on the diaphragm and potential displacement of abdominal organs. Exclusion criteria also include lack of cognitive ability to complete questionnaires, mobility impairments, memory impairments and dementia. We will not exclude participants with comorbid depression or history of substance abuse, as we will be including depression in our analysis as well as to have a representative sample.

**Procedures:** Recruitment for 6-week trial: Study recruitment will take place in the clinics of MUSC as well as by telephone with patients across the MUSC Enterprise that meet the study inclusion/exclusion criteria and have granted authorized research contact permission in MyChart through the electronic 'opt in' EPIC designation. Participants may also be recruited by via referral during an admission for COPD exacerbation, or within the first 2 weeks after discharge. If additional participants are needed, advertisements will be placed at the clinics of MUSC and our team will accept referrals from any MUSC provider regardless of recent hospitalization. Referrals will be screened for eligibility by our study team. An advertisement is included in the IRB submission (see supplemental file "Advertisement").

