**Sample Size:** The purpose of this pilot study is not to confirm or refute hypotheses about treatment effectiveness (with corresponding emphasis on establishment of sufficient power for hypothesis testing); rather, we seek to demonstrate feasibility of the intervention and to obtain estimates of variability for the secondary outcome measures. Therefore, sample size was determined for pragmatic reasons rather than power (Leon, Davis & Kraemer, 2011). For this pilot study, we will recruit approximately 30 patients with COPD and, basing our estimated attrition on previous investigations, we anticipate that approximately 25 of these patients will complete all study-related visits. For this project's secondary aims (continuous outcome measures of self-efficacy, fatigue, and dyspnea), we use an in intent-to-treat analyses and 95% confidence interval (CI) estimates of the within group change scores (pre- to post-treatment) with precisions ranging from  $\pm 0.20$  to  $\pm 0.78$ . These correspond to estimated standard deviations of change scores of these variables, ranging from 0.5 to 2.0.

**Data Management.** Data report forms (DRF) for all data collection will be developed by the PI and study team. The Research Electronic Data Capture (REDCap) system provided through MUSC CTSA will be used to enter questionnaire and measurement data. REDCap is a secure, web-based application designed exclusively to support data capture for research studies. Only authorized study personnel will have access to the data tracking system. Data management including data quality assessment

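### Recruits from an exacerbation admission can enter with no set interval before baseline, and the planned within-group change, with no between-arm contrast, would count their recovery as RESP-FIT effect

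*Combined protocol and SAP*

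**What the plan says.** **Entry.** Section 8.0 lists recruitment in clinics and "via referral during an admission for COPD exacerbation, or within the first 2 weeks after discharge". The Procedures paragraph of Section 10.0 repeats it: "Participants may also be recruited by via referral during an admission for COPD exacerbation, or within the first 2 weeks after discharge". Flyers, clinic approaches, MyChart contact and provider referral bring in people with no recent exacerbation.

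**Eligibility.** The Section 5.0 inclusion criteria cover age, English, and either lung function ("Diagnosed with COPD (PFT values: FEV1/FVC <0.7 and FEV1% predicted < 80% - within the past 6 months") or an MMRC dyspnea score above 2. The exclusions cover pregnancy and the post-partum year, cognition, mobility, WiFi and "Unwillingness to wear physical activity tracker daily, follow protocol, and/ or attend study visits". Neither list, nor the participant description in Section 10.0, asks for stable disease or a minimum time since an exacerbation.

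**Effect measure.** Section 10.0 names the "within-participant effect size of the RESP-FIT intervention", to be obtained from a pretest and posttest. The Sample Size paragraph of Section 12.0 plans "95% confidence interval (CI) estimates of the within group change scores (pre- to post-treatment) with precisions ranging from" ±0.20 to ±0.78 and adds: "These correspond to estimated standard deviations of change scores of these variables, ranging from 0.5 to 2.0". The Statistical Analysis paragraph sets post-intervention measures against baseline. Its t-test and Wilcoxon sentence covers demographic and baseline clinical variables.

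**Control arm.** Allocation is 1:1, 15 per arm, against standard of care plus a Fitbit, stratified by gender and MMRC grade. Section 3.0 justifies the control group by the possible effect of the activity tracker itself.

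**The concern.** A person enrolled soon after an exacerbation may have baseline dyspnea, fatigue, questionnaire scores and respiratory pressures measured while still recovering, and the 6-week values after further recovery. A pre-to-post change within one arm cannot separate that recovery from the effect of training. Dyspnea and fatigue, the Aim 2 symptoms, and activity, the Aim 4 outcome, are plausibly among the measures that move most. A temporary peak in dyspnea can also satisfy the MMRC route to eligibility and determine the MMRC stratum.

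Section 12.0 says the pilot is partly meant to yield variability estimates for the secondary outcomes, and Section 1.0 names a large efficacy RCT as the next phase. Effect sizes and SDs that contain recovery would carry over into that trial's design.

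**Working it through.** **Step 1: the plan's own precision.** Inputs from Section 12.0: SD of change 0.5 to 2.0, and about 25 completers of 30. Half-width = 1.96 × SD / √n.

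- n = 25: 1.96 × 0.5 / 5 = 0.196 and 1.96 × 2.0 / 5 = 0.784. These match ±0.20 and ±0.78.
- n = 12 or 13 (one arm): 0.283 or 0.272 at SD 0.5, and 1.132 or 1.087 at SD 2.0. These do not match.

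The stated within-group precision therefore pools the completers of both arms. In SD units it is 1.96 / 5 = 0.39. For a single arm it is 0.54 to 0.57.

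**Step 2: shift in mean change (assumed inputs).** Let f be the share of an arm recruited around an exacerbation, and r their mean natural recovery in units of the SD of change. The documents give neither. Shift = f × r.

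| f | r | Shift (SD) | SD multiplier √(1 + f(1−f)r²) |
|---|---|---|---|
| 0.25 | 0.5 | 0.125 | 1.02 |
| 0.25 | 1.0 | 0.25 | 1.09 |
| 0.50 | 0.5 | 0.25 | 1.03 |
| 0.50 | 1.0 | 0.50 | 1.12 |

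The shift is 22-92% of the single-arm half-width (0.125/0.566 to 0.50/0.544). With f = 0.10 and r = 0.25 it is only 0.025 SD, which is negligible.

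**Step 3: effect on a within-arm interval.** Suppose training has no effect. The probability that a nominal 95% t interval with 12-13 completers excludes zero is then:

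- about 7% at a shift of 0.125 SD;
- 12-13% at 0.25 SD;
- 35-38% at 0.50 SD, or 29-32% once the 12% increase in SD is included.

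**Step 4: the between-arm contrast.** Randomization makes f and r equal in expectation, so the expected bias of the difference in change is zero. Chance imbalance remains: the SD of the difference in f between two arms of 15 is √(f(1−f) × 2/15), which is 0.158 at f = 0.25 and 0.183 at f = 0.50. Multiplied by r, that is at most about 0.18 SD over the range in Step 2.

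The half-width is the critical value × SD × √(1/12 + 1/13):

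- z: ±0.39 to ±1.57 for SD 0.5 to 2.0;
- t: ±0.41 to ±1.66.

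This is about twice the stated ±0.20 to ±0.78.

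**The case against.** **The trial is randomized.** Both arms have the same expected recovery, all dependent variables are collected in everyone (Section 10.0), and the control arm would show the recovery. This stands, and it locates the fault. The entry route harms the estimate only because the effect is defined within participants or groups. Calling the design controlled does not supply the missing contrast.

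**Baseline may fall later than referral.** Consent is arranged at the patient's convenience and baseline takes place at the research center, so nobody need be measured at their worst. The qualifying lung function test may be up to 6 months old. This also stands: baseline timing is unknown. But no minimum is set, so early baselines are allowed.

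**Exacerbation history is already collected.** Section 10.0 lists self-reported hospitalizations and exacerbations, and records of exacerbation frequency and duration. Some description by recent status may be possible. Days since the last event are not specified, however, and neither the strata nor any planned analysis uses this history.

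**The larger SD may be the right one.** If the next trial recruits the same mix, variation in recovery belongs in its SD. This is fair; the inflation misleads only if the mix differs. Reporting the SD by status serves either case.

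**A stable-disease criterion is the obvious remedy.** A reader might infer that eligibility must be tightened. The documents do not support this as a requirement. Section 1.0 describes the app as growing out of post-discharge calls, and Aim 3 includes follow-up questions after a recent discharge, so these patients belong to the intended population. Such a criterion alone would also leave tracker effects and regression to the mean inside the within-group change.

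**Conclusion.** The concern holds in a limited form. The protocol combines a recruitment route around exacerbations, no interval before baseline, and an effect defined as within-participant or within-group change. Natural recovery in those recruits would be included in the reported RESP-FIT effect size and would add to its SD.

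The size cannot be fixed from the documents. Under the assumed shares and recoveries the shift is 0.13-0.50 SD and the SD inflation 2-12%; with few such recruits it is negligible.

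Two stronger readings are not supported. One is that the trial cannot separate recovery from training: it can, in expectation, by comparing change between arms. The other is that chance imbalance between the arms biases that comparison: it is ordinary sampling variation, already reflected in the width of the interval.

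The primary outcomes (satisfaction, fidelity, adherence) are not affected by this mechanism. The harm is to the secondary effect and variability estimates.

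**What to change.** 1. In Section 12.0, make the between-arm difference in baseline-adjusted change, with its 95% CI, the effect estimate for the secondary outcomes. Present within-group change as descriptive only, and align the effect-size wording in Section 10.0.
2. Record days since last exacerbation or discharge at baseline.
3. Report change and its SD by arm and by recent-exacerbation status.
4. Restate the expected precision for the between-arm difference.

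**Cost.** One baseline field and a few lines of analysis text, with no extra participants or visits. The interval is about twice as wide: roughly ±0.4 to ±1.6 with 12 and 13 completers. That figure is for the unadjusted difference in change; baseline adjustment may narrow it somewhat. Subgroup SDs will be imprecise at this sample size and should be read as descriptive.

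Whether to require a stable interval before baseline, and how long, is a separate decision for the investigators. It would reduce recovery at baseline, but at the price of delaying or losing recently discharged patients whom the program is partly meant to serve.

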## 7.0 Setting

This is not a multi-site trial. All aspects of this study will take place on-campus at MUSC or at the participant's place of residence. Informed consent will be conducted in the privacy of a patient room. The initial baseline and final study visits will occur at SCTR Nexus Research Center. All other study visits will be conducted either electronically over the tablet or by phone with the participant at their place of residence.

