### Objective Measures:

| Data Collection   | Measures   | Data sources and time points  |
|---|--|---|
| Demographics  | Age, health history, race/ethnicity, rural/urban residence, insurance  | Participant interview and medical records   |
| Clinical Characteristics                                    | FEV1/FVC
Self-reported hospitalizations/exacerbations   | Participant interview and medical records; PFT baseline and at second study visit |
| Maximal Inspiratory & Maximal Expiratory Pressure Generated | MIP and MEP recorded using a calibrated MicroRPM respiratory pressure meter, units in cm H 2 O ; a surrogate parameter for respiratory muscle weakness/strength | Collection and calibration at baseline, and at second study visit.                |
| Physical Activity: Steps                                    | # of steps taken daily (via Fitbit Alta)   | Daily   |
| Physical Activity: Patterns of Active Minutes               | # of minutes active throughout the day (via Fitbit Alta)   | Daily   |
| Sleep   | Hours of Sleep (via Fitbit Alta)   | Daily   |

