**Randomization and Training Regimen:** Following collection of pre-training baseline measures, participants will be randomly assigned 50/50 to either a Standard of Care (SOC) Control Group (n=15), or a SOC + EMST/IMST Group (n=15). Participant randomization will be stratified by gender and dyspnea grade as measured on the MMRC. Those participants assigned to the SOC control group will receive a Fitbit monitoring device, but no intervention beyond that which is typically provided to patients seen within the MUSC Clinic. Participants randomly assigned to receive SOC+EMST/IMST will receive six weeks of clinician-guided, scripted RMST. This training will be facilitated by the PI using a custom-designed and constructed EMST/IMST trainer. Non-invasive measurement of maximum expiratory and inspiratory pressures (PEmax and PImax; described previously) will be obtained in order to set pressure threshold of the EMST/RMST device. The first week of EMST/IMST training will be conducted with the device set at 75% of the average initial PEmax collected at pre-training baseline. After a nose clip is placed the participants will be taught a four-step procedure: 1) take a breath in, 2) wrap lips tightly around the EMST/IMST trainer mouthpiece, and 3) exhale quickly and forcefully until you hear the popping or whistling sound of the device valve opening, and 4) continue blowing forcefully for two seconds. Once the participant is able to do a five-breath trial, another five-breath trial will be completed with the participant allowed as much independence as appropriate. The participant will receive a text message each day reminding them to complete his or her training and "remain active today." Participants in the SOC group will receive a text message reminding them to "remain active today." The daily training session will be as follows: 1) five sets of five-breath exhalations (25 breaths total) completed each training day, 2) each exhalation within a set will be separated by approximately one minute, and 3) each five-breath training set will be separated by five minutes. A Bluetooth-enabled "use" button on the EMST/IMST device will log the times the participant has used their training device. Each participant will be provided with a diary to record five sets of five-breath training trials on five days each week. Our experience indicates that EMST/IMST takes approximately 20 minutes each day. PEmax will be reassessed weekly, by the research clinician across the six-week treatment period and readjusted to 75% of the participant's current PEmax. If no changes in PEmax are observed week to week, treatment

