
will be continued without increase in the pressure threshold training level. All participants will be managed according to standard treatment protocols used within the MUSC Pulmonary Clinic. Detailed records will be kept pertaining to mortality and morbidity as well as use of inpatient and outpatient hospital facilities, medication use, frequency and duration of disease exacerbations, as well as general response to treatment. All dependent variables will be obtained, for all participants at baseline, mid-intervention (3 weeks post baseline), at intervention end (6 weeks) and 14 weeks (2 months) post baseline.

**Monitoring period:** As per our standard monitoring period with SAMS, participants will receive a daily EMA reminder text. Answering the EMA questions on a smartphone requires 30-45 seconds of time. Probes will occur to not interfere with typical sleep schedule or during school hours. EMA sessions will capture COPD symptoms and emotion/mood over the course of the day. If patients have not filled out an EMA in 3 days, a reminder text will be sent. EMA probe question responses will transfer to RedCap, as TACHL has done with other studies. Data will not be stored on the phone. The participants will be requested to perform video capture of training technique 1 time per week. A reminder will be sent during convenient waking hours if this has not been performed.

**Activity Tracking:** A Fitbit activity tracker will be provided to each participant and comprehensive instruction offered on its use. This activity tracking device is worn on the wrist and only removed for bathing or other activities involving water, as the devices are water-resistant but not waterproof.

**Quantitative and Qualitative Assessments:** Participants will complete quantitative and qualitative assessments of acceptability, feasibility, and performance of the SAM system including:

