## 12.0 Data Management

**Statistical Analysis:** Primary analyses for this pilot feasibility study center on patient satisfaction, treatment fidelity and adherence, with a secondary focus on changes observed on fatigue and dyspnea scales (obtained from the SGRQ), PImax and PEmax change, physical activity (steps per day and active hours per day), physical activity engagement (PROMIS activity engagement scale), and sex based differences. Treatment satisfaction will be measured qualitatively through analysis of recorded post-intervention interviews. Training frequency will be automatically assessed by the Bluetooth enabled tracker, which will also be developed to measure pressure changes to evaluate treatment gains for PImax and PEmax. Pre- and post-intervention data will be analyzed for correlation between symptom severity and respiratory muscle strength (PImax and PEmax) along with mean steps per day. Post-Intervention data collection will include PEmax, PImax, PROMIS and SGRQ scales (see above) to compare to baseline measures. The sample will be characterized using descriptive statistics for all variables, as appropriate. T-tests or non-parametric Wilcoxon rank sum tests will be used to compare continuous demographic and baseline clinical variables and chi-square or Fisher's Exact Test will be used for categorical (e.g., survey responses). An overall indicator of acceptability/usability will also be a) adherence via a % of total EMA assessments completed. Comparisons between device use and reported affective states, stress levels, COPD symptoms over previous 1-2 days will also be examined. We will also gather information from the post-trial interviews via qualitative analyses on aspects of the SAM program that would benefit from refinement. Qualitative data will be presented as themes of domains relevant for refinement of SAM. Exploratory Quantitative Analyses: Nonparametric analyses will compare emergency department visits and hospitalizations with SAMS EMA question responses. Comparisons will be run on EMA ratings and training use.

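### Weekly PEmax retesting, by its purpose confined to the training arm, mixes test familiarity into that arm's PEmax gain; both arms need one standardised outcome measurement

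*Combined protocol and SAP*

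**What the plan says.** Specific Aim 2 (Section 1.0) lists PImax and PEmax among the outcomes for early signs of efficacy. Section 12.0 (Statistical Analysis) places "PImax and PEmax change" in its secondary focus and compares post-intervention values with baseline.

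Three parts of Section 10.0 bear on how often the pressures are measured:

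- **Training arm.** Under Randomization and Training Regimen, "PEmax will be reassessed weekly, by the research clinician across the six-week treatment period", and the device is then "readjusted to 75% of the participant's current PEmax".
- **Control arm.** The same text says: "Those participants assigned to the SOC control group will receive a Fitbit monitoring device, but no intervention beyond that which is typically provided". No trainer and no weekly pressure test are described for this arm.
- **Everyone.** The Objective Measures table gives the schedule for maximal inspiratory and expiratory pressure as "Collection and calibration at baseline, and at second study visit". The compensation text places Visit 2 at week 6. The methods text gives a fuller schedule: "All dependent variables will be obtained, for all participants at baseline, mid-intervention (3 weeks post baseline), at intervention end (6 weeks"), and again at 14 weeks.

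Section 7.0 puts the baseline and final visits at the research centre and adds: "All other study visits will be conducted either electronically over the tablet or by phone with the participant at their place of residence".

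The first week's device setting uses an average of the initial PEmax values, which suggests more than one baseline effort. The plan does not say how many efforts are made or whether they must agree. It requires no practice before baseline and no equal number of manoeuvres in the two arms. It also does not separate device-setting readings from outcome readings.

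**The concern.** A maximal pressure reading depends on how hard the participant tries, how the effort is coached and how familiar the manoeuvre is. If the baseline reading is unpractised and the week-6 reading follows several coached repeats, part of the rise reflects learning the test. The arm that repeats the test more often gains more from this, and here that is the training arm.

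The within-arm change carries the whole of the learning gain. Any comparison between arms would carry the excess over what controls learn. Both errors favour training. At stake is how far the PEmax result can be read as muscle strength, in a pilot meant to prepare a larger efficacy trial.

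**Working it through.** **1. The plan's own figure.** Section 12.0 (Sample Size) gives 95% CI half-widths of ±0.20 to ±0.78 for within-group change, with SDs of change from 0.5 to 2.0. These follow from 1.96 × SD / √n with n = 25, the expected number of completers:
- 1.96 × 0.5 / 5 = 0.196
- 1.96 × 2.0 / 5 = 0.784

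The figures reproduce, but they are stated for self-efficacy, fatigue and dyspnea. The plan gives no baseline, SD of change or practice effect for PEmax.

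**2. Who is tested weekly.** The stated purpose of the weekly test is to reset the trainer. Only the SOC + EMST/IMST arm has one, and controls receive a Fitbit and usual care. That weekly testing is confined to the training arm is an inference from purpose, not a statement in the protocol.

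**3. PEmax test occasions up to and including week 6.**

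| Arm and source | Count | Occasions |
|---|---|---|
| Training, weekly reassessment | 1 + 6 | 7 |
| Control, Objective Measures table | baseline + second visit | 2 |
| Control, methods text | baseline + week 3 + week 6 | 3 |

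The excess in the training arm is 7 − 2 = 5 or 7 − 3 = 4 occasions. The 7 is approximate, because the protocol does not list the weekly dates.

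**4. Other exposure to similar efforts.** The regimen prescribes 25 forceful exhalations a day, 5 days a week, for 6 weeks: 25 × 5 × 6 = 750. These resemble the PEmax manoeuvre, so trained participants would become familiar with forceful expiration even without weekly tests.

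**5. Direction and size.** More practice in the training arm pushes its change upward, so the direction follows from the counts and from the effort-dependent nature of the test. The size in cm H2O does not follow from anything in the documents.

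**The case against.** The strongest reply is that the weekly tests are a small part of the practice. About five interim tests add little to 750 training exhalations, and familiarity with forceful expiration is arguably part of the intervention. This stands in part: no measurement rule can remove familiarity gained through training. The coached weekly tests are still a separate source, and bringing everyone to a reproducible baseline leaves less to be learned from either.

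A second reply is that the weekly schedule is itself uncertain. Section 3.0 describes adjustments timed by feedback, in contrast to simple weekly increases, and Section 7.0 has visits other than baseline and final held by tablet or phone. That weakens the exact count and strengthens the case for reconciling the text.

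Third, this is a pilot. Primary analyses concern satisfaction, fidelity and adherence, and Section 12.0 disclaims any test of effectiveness. This stands, and it sets the severity.

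Stronger readings that a reader might infer do not hold:

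- **A calculated false-positive rate.** The plan states no between-arm test of PEmax, and such a rate depends entirely on assumed inputs. Suppose there is no true effect and an assumed gain of 15 cm H2O in trainers that controls do not share. A two-sided 5% t-test would then reject in 75% of trials with an assumed SD of 15 and 15 per arm, but in 30% with SD 25 and 12.5 per arm (25 completers / 2). With an assumed gain of 3 cm H2O the range is 6–8%. Controls also repeat the test, so treating the whole gain as a between-arm difference overstates it.
- **The same bias in PImax.** Weekly retesting is stated for PEmax only.
- **An outcome reading taken by the trainer.** The documents do not say who takes the week-6 reading.
- **An inflated signal passed on to the next trial.** The documents do not use PEmax to size or justify that trial.

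**Conclusion.** The point holds as a minor one. Followed as written, the plan gives the training arm about 7 PEmax test occasions by week 6, against 2 or 3 in controls. No practised, reproducible baseline is required. The training arm's pre-post PEmax change therefore cannot be read as strength gain alone, and the error favours training.

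This rests on the inference that weekly testing is confined to the arm with the device, and on PEmax being effort-dependent. The size is unknown, and part of the familiarity is inseparable from the training. The primary feasibility results are unaffected.

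**What to change.** 1. At baseline, before randomisation, and again at week 6, measure PEmax and PImax in both arms with one script. Repeat the manoeuvre until the best efforts agree within a tolerance fixed in advance, and state which value is recorded.
2. Name these readings as the only PEmax and PImax outcomes. Use the weekly readings for device setting alone. This leaves the device-setting procedure unchanged.
3. Where existing staff allow, have someone other than the training clinician take the week-6 reading.
4. Reconcile the pressure-measurement schedules in the Objective Measures table, the weekly reassessment text and the all-participants schedule in Section 10.0. State whether controls are tested between baseline and week 6, and how any interim reading is obtained, given the remote visits in Section 7.0.
5. When reporting, say that some familiarity from training remains in the PEmax change.

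The cost is a change of wording plus some extra minutes and participant effort at two existing visits. The fix reduces the bias but does not remove it: weekly tests continue in one arm, and training still resembles the test.
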